1. PURPOSE OF STUDY

Specific Aim 1. To test the feasibility of evaluating the efficacy of TENS for chronic edema in a single-site, single arm study.

Specific Aim 2. To estimate the potential effects of TENS on swelling (via tape measurements water volume displacement, and patient-reported swelling) pain, heaviness, weakness, discomfort, patient satisfaction with the treatment, self-reported ability to be active, quality of life, activity (measured via activity tracker), lower limb sensation, and ankle range of motion.

2. BACKGROUND AND RATIONALE

Chronic edema of the lower limbs (i.e., chronic peripheral edema) is a common condition. Peripheral edema can cause pain, heaviness, weakness, discomfort, negative body image and limit mobility and flexibility. Limitations to mobility can reinforce a sedentary lifestyle, which exacerbates peripheral edema, leading to a vicious cycle of disease. Furthermore, when peripheral edema is untreated, it causes increased risk of infection and ulcers.² Nineteen percent of older US adults surveyed in the 2016 wave of the Health and Retirement Study³ reported persistent lower limb swelling (manuscript in preparation). It affects many individuals, including those with obesity, older age, sedentary lifestyles, history of deep venous thrombosis, and occupations that require long periods of standing.^{4,5} Considering the high rates of obesity in the US, peripheral edema is a large and likely growing public health challenge.⁴ No cure for peripheral edema exists. Some types of edema are responsive to diuretics,⁴ but these medications cause frequent urination. Dietary restrictions, such as limiting salt intake, can reduce edema as well. However, lifestyle changes are challenging to implement and sustain, especially for lower income patients for which easy access to whole foods is lower. Compression stockings are generally accepted as the standard of care treatment to contain swelling associated with edema. However, many patients find compression stockings to be uncomfortable or even painful, embarrassing, hot in the summer, and itchy. Taken together, improved treatments for chronic peripheral edema are highly warranted.

Peripheral edema is caused by increased interstitial fluid volume. The interstitial fluid volume is controlled by a delicate balance between hydrostatic pressures in the plasma and interstitial space, which are controlled by the venous and lymphatic systems. Underlying health conditions affect fluid (i.e., water and dissolved solutes) flow out of the arterial end of the capillaries into the interstitial space. The majority of this fluid is reabsorbed back into the venous end of the capillaries. The remaining net increase in interstitial fluid is removed via the

Page 1 of 26

lymphatic system. An increase in capillary pressure, due to insufficient venous return of blood, can cause increased bulk flow of fluid into the interstitial space. This increased bulk flow can overwhelm the lymphatic system leading to the inability to absorb, which causes peripheral edema. In addition, deficiencies in the lymphatic system can lead to peripheral edema by collection of the normal excess of fluid that flows from the capillaries into the interstitial space.⁶

Chronic venous insufficiency (CVI) is a common condition that is characterized by decreased venous return of blood that leads to venous hypertension in the lower limbs. A large population-based study found the prevalence of CVI to be 9.4% in men and 6.5% in women.⁵ Decreased venous return is often caused by venous valve dysfunction, which can be caused by poor venous tone preventing the valves from closing completely to stop reflux of blood to the lower limbs. Hypertension in the capillaries of the lower limbs leads to increased hydrostatic pressure and fluid leakage and edema. Long-term hypertension negatively affects capillary tone, further exacerbating fluid leakage and edema.² Furthermore, venous hypertension has been linked to increased inflammation that can further exacerbate impairments in venous tone.² Thus, interventions that can improve venous tone could improve edema from CVI. In fact, a micro-ionized purified flavonoid fraction pharmacotherapy that can improve vascular tone has shown promise in improving CVI.⁷

Transcutaneous electrical nerve stimulation (TENS) is electrical current that is delivered through the skin. It is a safe, non-pharmacologic treatment that is commonly used to treat chronic pain. TENS has been reported to improve peripheral edema in a case series (n=3)⁸ as well as in a small clinical trial that compared TENS to usual care (n=10).⁹ It was also found to decrease swelling associated with complex regional pain syndrome in a small RCT.¹⁰ In addition, our preliminary data (see Preliminary Data Section below) showed a marked improvement in peripheral edema for 3 individuals who used TENS daily for 1 to 3 weeks. TENS has been shown to stimulate the autonomic nervous system.¹¹ Thus, TENS could stimulate the autonomic nerves causing improvement in capillary and venous tone, which could decrease fluid leakage from capillaries as well as promote more efficient venous return leading to decreased lower limb venous hypertension. In turn, decreased lower limb venous hypertension could lead to decreased inflammation. TENS could also cause sufficient muscle contractions to sufficiently decrease the diameter of the veins to improve venous return, although high frequency TENS used in our preliminary data does not cause perceptible muscle contractions.

Because TENS can also improve pain and is a non-pharmacologic treatment, it could be an ideal therapy for peripheral edema that it is often accompanied by pain and occurs in patients with co-morbid conditions that may already have challenges with polypharmacy. The goal of this proposal is to evaluate the feasibility of studying daily TENS therapy for peripheral edema in patients with chronic venous insufficiency and evaluate its preliminary efficacy. If the results of this initial trial are promising, the data will be used to obtain funding to support a larger efficacy study that can incorporate outcomes to investigate the efficacy of the therapy and potential mechanism related to improvements in venous tone.

Page 2 of 26

Preliminary data

4. STUDY DESIGN

Experimental design

This study is single center, subject will receive a wireless TENS device. The treatment period will be 3 weeks in duration. All subjects will be allowed to keep the commercially-available device for use after the study. All subjects will be called (via phone) one month after completion of the Endpoint visit and asked if they are still using their commercial device.

The study will have a single arm. The coordinator will introduce the study device, be available to answer questions about the device, and assess adverse events. Subjects will be told that we are testing whether TENS, which has shown promise in some patients but needs to be tested formally, has an effect on lower limb swelling.

Page 3 of 26

Study measures

Demographic data will be collected from the medical record including age, sex, BMI, medications they are taking that could affect lower limb edema, history of diabetes, cancer, deep vein thrombosis, post thrombotic syndrome, peripheral neuropathy, and hypertension.

Feasibility (primary)

- (1) Screen failure and patient refusal rates will be assessed using study records.
- (2) Outcome measure completion rates will be assessed using study records.

Feasibility (secondary)

(1) Treatment adherence will be evaluated using data from the TENS device's Quell App (i.e., the number of treatment sessions/day and the time that the device was in contact with the skin). The Quell Health account within the Quell App for each subject will be setup at the Baseline visit using a de-identified, unique dummy email address created for the study to protect subjects' privacy.

Feasibility (exploratory)

(1) Potential reasons for low treatment adherence will be captured using structured qualitative interviews and used to assess potential reasons for low adherence and ways to improve a future study.

Potential Efficacy (primary) Objective

assessments:

(1) Swelling The volume of water displaced by the combination of the foot and ankle, and the entire lower limb below the knee of the most affected limb at baseline will be measured using a Volumeter, which is a water displacement measurement device. The volumes will be recorded in **Volumeter Measurements** form.

Volume measurements have been used in a successful trial of compression stockings for flightinduced peripheral edema. 12

Patient reported outcome measure (PRO):

(1) Swelling and symptoms associated with edema will be recorded in the Edema Symptom Daily Diary using a verbal rating scale (VRS) of swelling in the lower limbs and feet using the anchors "none", "a little bit", "quite a bit" "a lot", or "very much", [1 = none, 5 = very much]. The subject will also be asked to rate these symptoms, while thinking about the past week using the Edema Symptom Inventory-Week Recall, which uses the same scale as the diary and the Edema Symptom Inventory-Week Recall 0 – 10 Scale which uses 0 – 10 numerical rating scale (NRS) [0 = not at all, 10 = worst imaginable].

Potential Efficacy (secondary) Objective

assessments:

Page 4 of 26

(1) Swelling. The coordinator will use a tape measure at the arch of the foot, 1/2 and the distance between the middle of the kneecap and the ankle, and at the knee crease of both limbs regardless of which is more affected. Measurements will be recorded in the **Coordinator Lower Limb Swelling** form. Tape measurements have been used in a successful trial of compression stockings for flight-induced peripheral edema.¹²

Patient reported outcome measures (PROs):

- (1) Changes in symptoms, activity, and emotions will be recorded in the **Impression of Change in Edema Symptoms** form that uses a verbal rating scale (VRS) asking subjects to report whether they have experienced changes in the symptoms. The scale uses the anchors "very much improved", "much improved", "minimally improved", "not changed", "minimally worse", "much worse", or "very much worse" [1 = very much improved, 7 = very much worse].
- (2) Quality of Life will be assessed using the Lymphoedema Quality of Life Tool (LYMQOL) using a verbal rating scale (VRS) with anchors "not at all", "a little bit", "quite a bit", or "very much [1 = not at all, 4 = very much]. If the question is not applicable the measurable scale value is 0. Overall quality of life (Q22) is measured using a 0 10 numerical rating scale NRS scores [0 = poor, 10 = excellent]. The LYMQOL was developed based on interviews with patients. The initial validation study found reasonable Chronbach's alpha for items and criterion validity when compared to a general measure of quality of life. 13

Potential Efficacy (exploratory) Objective

assessments:

- (1) Lower limb sensation will be measured using a monofilament threshold test (i.e., lower limb sensation test)¹⁴ on the most affected limb at baseline. The scores will be recorded in the **Lower Limb Sensation Test Scoring Sheet**.
- (2) Activity will be measured using the number of steps taken and period of time the subject is sedentary with a Fitbit activity tracker and the TENS device's Quell App.
- (3) Ankle range of motion will be measured using a tape measure while the subject performs the weight-bearing lunge. The resulting measurements will be recorded in the **Ankle Range of Motion** form. This method has been shown to have good reliability when administered by a novice rater.¹⁵

Patient reported outcome measure (PRO):

(1) Fatigue will be assessed using the **PROMIS Fatigue** – Short Form. The PROMIS Fatigue – Short Form was created using a multisite project developed by a clinically relevant and psychometrically quality of life assessment tool for adults and children with neurologic disorders. The measure uses a verbal rating scale (VRS) with anchors "never", "rarely", "sometimes" "often ", or "almost always" [1 = never, 5 = almost always].

Page 5 of 26

Mood, Stigma, and Sleep will be assessed using modified version of Chronic Venous Disease Quality-of-Life Questionnaire (CIVIQ 20), which was developed based on a clinically relevant and psychometrically quality of life assessment tool for adults. The validity was assessed using Cronbach's alpha coefficients and multi-trait/multi-item matrix analyses. The CIVIQ 20 consists of a VRS asking subjects to report whether they have experienced any of specific emotions over the past three weeks using a 1 – 5 Likerttype scale, with anchors "not at all", "a little", "moderately", "a lot", or "completely" [1 = not at all, 5 = completely].

Single-Item Questions:

- (1) **Expectation Questionnaire**. The subject's expectation of device efficacy will be assessed by asking the subjects: "How much do you expect the TENS device will improve your edema symptoms?" using a 1-5 Likert-type scale, with anchors "not at all", "a little bit", "quite a bit", "very much", or "completely" [1 = not at all, 5 = completely].
- (2) General Impression of change in Edema. The subject's impression of change in edema symptoms will be measured using a single question (i.e., General Impression of Edema form) that utilizes a 1 7 scale adapted from the patient global impression of change (PGIC). ¹⁸ The scale uses the anchors "very much improved", "much improved", "minimally improved", "not changed", "minimally worse", "much worse", or "very much worse" [1 = very much improved, 7 = very much worse]. The PGIC is commonly used in chronic pain trials to assess subjects' experiences of the change from the beginning of a treatment or clinical trial. ¹⁹
- (3) **General Impression of change in Activity**. Impression of change in ability to be active will be measured using a single question (i.e., **General Impression of Activity** form) that utilizes a 1 7 scale adapted from the PGIC.¹⁸ The measure uses the anchors "very much improved", "much improved", "minimally improved", "not changed", "minimally worse", "much worse", or "very much worse" [1 = very much improved, 7 = very much worse]. The PGIC is commonly used in chronic pain trials to assess patients' experiences of the change from the beginning of a treatment or clinical trial.¹⁹

Subjects will record the medications taken for edema each day on the **Edema Symptom Daily Diary**. The coordinator will ask the subject if they take certain medications known to affect swelling and if they take any medications to treat their peripheral edema. The coordinator will customize the medication diary portion of the **Edema Symptom Daily Diary** to include these medications only.

A qualitative interview will be performed to explore how subjects prefer to rate the symptoms associated with peripheral edema, what additional symptoms were not asked about, and what aspects of the subject's life are affected by their edema. The responses will be recorded on the Treatment **period Endpoint-Qualitative** forms.

Page 6 of 26

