Page 15 of 26

Table 3: Edema schedule of data collection.

| FORMS | Screening | Prebaseline period | Treatment period | Treatment period Endpoint |
|---|-----------|-----------------------|------------------|---------------------------------|
| Subject Forms (REDCap or paper) | | | | |
| On Study | | X | | |
| Edema Symptom Daily Diary | | | X | X |
| Edema Symptom Daily Diary-Pre-baseline ¹ | | X | | |
| Impression of Change in Edema Symptoms | | | | X |
| Expectation Questionnaire ³ | | | X | |
| CIVIQ 20 ³ | | | X | X |
| LYMQOL ³ | | | X | X |
| PROMIS Fatigue ³ | | | X | X |
| Edema Interference Questionnaire ³ | | | X | X |
| General Impression of Edema ³ | | | | X |
| General Impression of Activity ³ | | | | X |
| Edema Symptom Inventory-Week Recall | | X | X | X |
| Edema Symptom Inventory-Week Recall 0-10 Scale | | X | X | X |
| Treatment period Endpoint-Qualitative Feedback | | | | X |
| Coordinator Forms (REDCap or paper) | | | | |
| Eligibility checklist (Medical record, Clinicianreported, and Patient-reported items) ¹ | X | | | |

Page 16 of 26 Version Date: 12/8/2020

| Consent form | X | | |
|--------------------------------------|---|---|---|
| Clinical Record Information | X | | |
| TENS Device Settings | | X | |
| Coordinator Lower Limb Swelling | X | X | X |
| Volumeter Measurements | | X | X |
| Lower Limb Sensation Threshold | | X | X |
| Ankle Range of Motion | | X | X |
| COVID pre-screen form | X | X | X |
| Telephone Contact | X | X | X |
| Adverse Event (AE) form ² | | | X |

¹ Forms are completed during the weeks 1, 2, and 3 and being returned by mail to the research team.

General policies regarding contacting subjects: If subjects have chosen to be contacted by email but do not respond to email reminders, they will be called up to 2 times for that specific reminder. If a subject does not attend a phone Call or in-person visit, they will be called up to 3 times to try and reengage the subject in the study. If any phone calls are interrupted or stopped short for any reason, including technological difficulties, a subsequent phone call will be setup to complete the necessary research tasks. Rescheduling of visits can occur up to 1 week after the original visit was scheduled, which will be scheduled within the time-frame indicated in the protocol section for each visit.

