The only difference between the commercially-available TENS device's programming and the study TENS device is the size of the intensity increase with a button tap. The maximum allowable intensity is the same as the commercially-available TENS device. Thus, there is no major safety concern if a subject fails to return to the study and continues to use one the study devices, therefore no further attempts other than those outlined above will be made to contact subjects to retrieve the study TENS devices to minimize intrusion in subjects' lives.

Page 17 of 26

² Adverse events will also be assessed after Week 1 via phone

³ Form can be completed via REDCap by subject prior to or at Visit 1, Visit 2, and Visit 3

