16. DATA ANALYSIS PLAN

Missing Data

All efforts will be made to prevent missing data. Due to the exploratory nature of the study, missing data will not be accommodated statistically.

Sample Size Estimation

We plan to recruit 52 people for this study because it is what we think is feasible given our resources and should provide sufficient information to determine whether there is a reasonable potential efficacy signal to move forward to a randomized clinical trial.

Aim1. Feasibility Analyses

(1) Descriptive statistics will be used to summarize all feasibility outcomes. (2) Common themes in subject-reported reasons for low adherence will be summarized in the qualitative data.

Aim 2. Preliminary Efficacy

- (1) Primary preliminary efficacy: Preliminary efficacy for the water volume displacement outcome and the Edema Symptom Daily Diary will be assessed using Wilcoxon sign-ranked test comparing the outcomes from Baseline and Treatment Endpoint.
- (2) Secondary preliminary efficacy: Similar analyses to those in the primary preliminary efficacy aim will be used for the secondary efficacy outcomes.

Due to the exploratory nature of the study, no adjustments will be made for multiplicity.

Exploratory Analyses

- 1) Similar analyses to those in the primary preliminary efficacy aim will be used to assess changes between Baseline and Treatment Period Endpoint for the continuous exploratory efficacy outcomes.
- 2) The percentage of subjects whose monofilament threshold improves between Baseline and Double-blind Endpoint will be compared using a Fisher's exact test.
- 3) Trajectories of changes in activity (measured via the Fitbit) and changes in swelling (measured via NRS swelling and symptoms ratings) will be visually inspected and compared to investigate whether increased activity precedes and therefore may contribute to decreased swelling.
- 4) Qualitative analysis techniques will be used to analyze the cognitive interview data to improve self-report measurements for peripheral edema.

Page 24 of 26

5) We will explore the data for patterns to see if people with different causes of edema seem to benefit from the treatment more frequently than others. These qualitative analyses will be used to inform future entry criteria.

REFERENCES

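### In an uncontrolled study with a self-rated primary efficacy outcome, every subject hears a favourable cue about TENS, and the expectation score that is collected has no planned use and no secured pre-device timing

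*Combined protocol and SAP*

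**What the plan says.** - **Design and message.** Section 4, Experimental design: "The study will have a single arm". No sham, untreated group or blinding is described. The message to subjects begins "Subjects will be told that we are testing whether TENS, which has shown promise in some patients"; the same sentence goes on to say that formal testing is still needed, and ends by naming lower limb swelling as the outcome in question.
- **Outcomes.** Section 16, Aim 2: "Preliminary efficacy for the water volume displacement outcome and the Edema Symptom Daily Diary will be assessed using Wilcoxon sign-ranked test", comparing Baseline with Treatment Endpoint. The diary is rated by the subject; volume is measured by the coordinator.
- **Expectation item.** Section 4, Single-Item Questions, asks "How much do you expect the TENS device will improve your edema symptoms" on a 1-5 scale. Table 3 marks the form once, in the Treatment period column, and not at Endpoint.
- **Timing.** Footnote 3 to Table 3, shared by several forms, reads "Form can be completed via REDCap by subject prior to or at Visit 1, Visit 2, and Visit 3". Reminder 2 (in the week leading to Visit 2, although its heading names Visit 1) asks subjects to complete visit questionnaires online beforehand. The Visit 2 text lets those not yet done be completed at the visit, and sets no order relative to pairing and calibrating the device.
- **Analyses.** The only generic exploratory analysis is "Similar analyses to those in the primary preliminary efficacy aim will be used to assess changes between Baseline and Treatment Period Endpoint", for continuous exploratory efficacy outcomes. The other four exploratory items cover the monofilament test, activity against swelling, the interviews, and cause of edema. None names expectation.

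**The concern.** A subject who expects benefit may rate swelling and symptoms lower after three weeks whether or not the device works. With no comparison group, that shift enters the diary test in the direction counted as efficacy. The study's own message supplies part of the cue, and the favourable clause is not needed to explain what is being tested.

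The plan evidently regards expectation as relevant, since it collects a score, but it then leaves the score unused. By contrast, Section 16 does plan a look at one rival explanation, increased activity. A score that some subjects give before the device is explained and felt, and others after, would also be hard to interpret.

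At stake is how the signal is read. Section 16 says the study should show whether there is enough of an efficacy signal to proceed to a randomized trial, and Section 2 says promising data will support a funding application. A diary improvement driven partly by expectation could encourage that step without any caveat in the plan.

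**Working it through.** **1. Can any planned analysis use the expectation score?** The Section 16 template needs a Baseline and an Endpoint value. Table 3 gives the form one mark, so no change score exists. No other listed analysis mentions it. The score therefore has no stated use.

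**2. Is the form tied to a time before the device?** Reminder 2 makes completion before the visit the default. The Visit 2 fallback and footnote 3 allow later completion. The timing is mostly right by default but not secured.

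**3. How easily could a shift unrelated to TENS make the diary test significant?** The plan has no power calculation to reproduce. The figure of 52 rests on feasibility, and the only related arithmetic is the enrolment yield: 150/3 = 50, close to 52. The plan states neither alpha nor sidedness.

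Assumptions: zero TENS effect, normally distributed paired changes, two-sided 5% signed-rank test, and an expectation shift of d SDs of the within-subject change. Losing about 15% of subjects leaves 52 × 0.85 ≈ 44 pairs. Simulated rejection rates (5,000 runs per cell):

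| d | n=52 | n=44 |
|---|---|---|
| 0 | 4.7% | 4.6% |
| 0.1 | 11.3% | 9.4% |
| 0.2 | 28.1% | 24.0% |
| 0.3 | 55.0% | 48.9% |
| 0.4 | 79.1% | 71.9% |
| 0.5 | 93.8% | 89.0% |

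Normal-approximation check, Φ(d√n − 1.96): for d=0.3 and n=52, 0.3 × 7.211 − 1.96 = 0.203, giving 58.1%, close to the simulated 55.0%.

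**4. What could an analysis of the score show?** By Fisher's z with n=52, √(n−3) = 7.
- 95% half-width around r=0: tanh(1.96/7) = 0.27.
- Correlation detectable with 80% power: tanh((1.96 + 0.842)/7) = 0.38 (0.41 at n=44).
- Power at r=0.30: Φ(0.3095 × 7 − 1.96) = Φ(0.207) = 58% (51% at n=44).

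Two simulated cases (2,000 runs each, n=52), with assumed probabilities of 0.05, 0.20, 0.35, 0.30 and 0.10 for scores 1 to 5:
- Every subject shifts by 0.5 SD whatever the score: the diary test rejects in about 93% of runs, the Spearman test in about 4%.
- The shift grows by 0.225 SD per scale point above 1. The mean score above 1 is 2.2, so the mean shift is 0.225 × 2.2 ≈ 0.50 SD. The diary test rejects in about 92%, the Spearman test in about 34%. The regression estimate of change at the lowest expectation level has a standard error of about 0.33 SD, a 95% half-width of 1.96 × 0.33 ≈ 0.65 SD.

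A correlation near zero would therefore be compatible with a large expectation effect.

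**The case against.** The strongest reply is that the confounding comes from having no control arm, and would be the same if the score were analysed. That stands. A reader might infer that the missing analysis is why expectation could pass for a TENS effect, or that the questionnaire could have exposed the bias. The documents do not support either inference: all subjects hear the same message, and step 4 shows that a uniform shift leaves no correlation to find.

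Second, the message is more balanced than its first half suggests, because it also says that formal testing is needed. That stands too. It softens the cue but does not remove it.

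Third, the rejection rates in step 3 are the ordinary power of a signed-rank test against any mean shift from any cause. They do not measure what the wording does, and the documents contain nothing that would.

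Fourth, a reader might take a correlation with diary change but not with volume change as evidence of expectation. That does not follow. The diary covers associated symptoms and both lower limbs, while volume is taken on the most affected limb only; Section 2 notes that TENS can relieve pain; and expectation could act through adherence. Sampling error adds to this: if both true correlations were 0.30 and the tests were independent (an assumption), the pattern of diary significant and volume not would arise in 0.58 × 0.42 ≈ 24% of trials.

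Finally, Aim 1 is feasibility, efficacy is labelled preliminary, and the other primary efficacy outcome is a physical measurement less open to expectation, although no masking of the coordinator is described. This limits the harm. It does not explain why a score is collected with no stated use.

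**Conclusion.** The point holds as an inexpensive improvement. Expectation can contribute to a diary improvement and cannot be separated from a TENS effect in this design; the study's wording adds a favourable cue; and the expectation score is collected once, with loosely secured timing and no analysis. Under assumed shifts of 0.1 to 0.4 SD and no TENS effect, the diary test would be significant in about 11% to 79% of trials with 52 pairs. These figures rest on normal changes, a two-sided 5% test and shift sizes that the documents do not give.

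It does not follow that the wording causes a bias of any known size, that the volume outcome is affected to the same degree, or that the trial makes an unsupported confirmatory claim. The consequence is a possibly misleading go-ahead to a randomized trial, where expectation could be controlled.

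**What to change.** 1. In the Section 4 statement to subjects, drop the clause about earlier promise and say only that it is not known whether TENS affects lower limb swelling and that the study is testing this. Make the same change in the Visit 2 standardized script if the clause appears there; the script is not reproduced in the documents.
2. Require the Expectation Questionnaire to be completed before the device is introduced at Visit 2, and give it its own footnote in Table 3.
3. In Section 16, add a descriptive summary of the expectation score and its Spearman correlation, with 95% CI, with diary change and with water-volume change. Do not split the scale into low and high groups, and do not adopt a rule that a diary-only correlation indicates expectation.
4. State in Section 16 that a null correlation does not rule out an expectation effect, and that diary change cannot be attributed to TENS without a control.

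Cost: a sentence of wording, one timing instruction and a few lines of analysis on data already collected, with no new subjects, visits or instruments. Downside: the correlation will be imprecise (about ±0.27, with 80% power only at r of about 0.38), and neutral wording reduces expectation by an unknown amount without removing it.

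### LYMQOL answers of not applicable are given the value 0 on a 1-to-4 scale, and no rule keeps that 0 out of the score

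*Combined protocol and SAP*

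**What the plan says.** Section 4 (Study Design) lists the LYMQOL among the secondary efficacy patient-reported outcomes. Each item has four response options, numbered 1 for not at all through 4 for very much. The next sentence reads: "If the question is not applicable the measurable scale value is 0". The overall item, Q22, has its own 0-to-10 scale ("0 = poor, 10 = excellent"), on which 0 is a genuine answer.

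Tables 2 and 3 in Section 8 place the questionnaire at the baseline and endpoint visits. Section 16 (Data Analysis Plan) says: "Similar analyses to those in the primary preliminary efficacy aim will be used for the secondary efficacy outcomes". The primary analysis it points to "will be assessed using Wilcoxon sign-ranked test comparing the outcomes from Baseline and Treatment Endpoint". On incomplete data, Section 16 says only that "missing data will not be accommodated statistically".

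No section says how LYMQOL items are combined (single items, sum, mean over all items, or mean over applicable items). None states which end of the 1-to-4 scale is worse, or what happens to an item that is applicable at one visit and not at the other.

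**The concern.** The value given to a not-applicable answer lies below every real answer. The sentence calls it a scale value, not a code or a missing-data marker, so an analyst who follows it literally would enter 0 into the score. Any item-level, summed or all-item-mean score would then rank not applicable beyond not at all.

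If higher means worse, an item that stops applying between the visits registers as a gain in quality of life, and one that starts to apply registers as a loss. The study has one arm, so no control group would show the same drift and cancel it. The efficacy results are meant to inform whether a randomized trial is worth pursuing, and a secondary outcome that moves for coding reasons could mislead that decision.

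**Working it through.** There is no figure in the plan to reproduce. The protocol gives no LYMQOL score, SD, effect size or significance level, and the sample size rests on feasibility ("We plan to recruit 52 people for this study because it is what we think is feasible given our resources").

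**Inputs from the protocol.** Real item values 1 to 4; not applicable = 0 (Section 4). Paired Wilcoxon signed-rank comparison of baseline and endpoint; n = 52 (Section 16).

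**Assumptions.** Number of items K (5, 10 or 21), starting rating v, share of subjects who switch p (10% to 30%), higher = worse, and the 0 enters the score.

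**Step 1: one subject.** All K items are rated v at baseline, one becomes not applicable, and nothing else changes. The sum changes by 0 - v = -v, and the all-item mean by -v/K. A real improvement of one item from 3 to 1 changes the mean by -2/K.

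| K | 1 to not applicable | 3 to not applicable | real change 3 to 1 |
|---|---|---|---|
| 5 | -0.20 | -0.60 | -0.40 |
| 10 | -0.10 | -0.30 | -0.20 |
| 21 | -0.048 | -0.143 | -0.095 |

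Written out for K = 5: (3+3+3+3+0)/5 = 2.4 against 3.0, and (1+1+1+1+0)/5 = 0.8 against 1.0. The second result lies below the lowest value that real answers can give.

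**Step 2: the group mean.** If a share p of subjects has one such switch, all in the same direction, the mean moves by p × v/K. For K = 5:

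- v = 3: 0.10 × 0.6 = 0.06 to 0.30 × 0.6 = 0.18.
- v = 1: 0.10 × 0.2 = 0.02 to 0.30 × 0.2 = 0.06.

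**Step 3: the planned test.** A mean shift is not what a signed-rank test evaluates, so the test was simulated with no true change: n = 52, 2000 runs, 10% of items not applicable at baseline, all-item mean with 0 included, two-sided 5% level. The response distribution, rates and level are assumptions.

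| Share of applicable items that become not applicable, none returning | Rejections, 10 items | Rejections, 21 items |
|---|---|---|
| 2% | 15% | 24% |
| 5% | 55% | 86% |
| 10% | 97% | 100% |

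With balanced movement (2% of applicable items leave and 18% of not-applicable items return, so 0.90 × 0.02 = 0.10 × 0.18 = 0.018 each way), the mean shift is 0 and the rejection rate is about 5%. With not-applicable items left out of each visit's mean, the rejection rate is 4.6% to 5.8% in every scenario.

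**Step 4: why the same items should be used at both visits.** Leaving the item out at one visit only is enough when ratings are alike, but not in general. Take five items rated 3, 3, 3, 3, 1, where one of the 3s becomes not applicable:

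- 0 scored: 13/5 = 2.6 to 10/5 = 2.0, change -0.6.
- Items applicable at each visit: 13/5 = 2.6 to 10/4 = 2.5, change -0.1.
- Items answered at both visits: 10/4 = 2.5 to 10/4 = 2.5, change 0.

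**The case against.** The strongest reply is that the plan never says the 0 is added into anything. Section 4 describes response options; the 0 may be only a data-entry code, with such items dropped at scoring. The LYMQOL is a published instrument whose validation the protocol cites, and its own scoring convention may settle the matter. That source cannot be consulted here. This stands, and it makes the point conditional. It does not dispose of it: the protocol calls the 0 a scale value, uses 0 as a real score for Q22 in the same paragraph, and points to no outside rule for not-applicable items.

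Four further points also stand:

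- That higher is worse is a reasonable reading of the anchors but is not stated. If the direction were reversed, the 0 would still be an extreme value that no real answer can take.
- Switches can run both ways, and only a net flow biases the group comparison.
- The sizes above depend on assumed item counts, starting ratings and switch rates.
- An item that stops applying may reflect a real change in the subject's life, for instance an activity given up. The protocol does not define the response. The difficulty is that a scored 0 treats every such switch as better than the best real answer, whatever the reason for it.

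On consequence, this is one secondary outcome in a study that calls itself exploratory and states that "no adjustments will be made for multiplicity".

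**Conclusion.** The point holds in conditional form. The protocol assigns not applicable a value below the scale's lowest real answer and gives no rule that excludes it. If that value is scored, individual LYMQOL changes are distorted, and a net one-way flow biases the baseline-to-endpoint test. Under the 5-item assumption the distortion is 0.2 to 0.6 points for a subject with one switching item. It is about 0.02 to 0.18 points for the group mean if 10% to 30% of subjects switch in one direction. If flows balance, the group mean is unbiased; if the 0 is only a code, the artefact disappears.

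A reader might infer that the analysis will certainly count not applicable as improvement, or that any LYMQOL gain in this trial would be spurious. The documents support neither: they contain no combining rule, no stated scale direction, and no information on how often or in which direction items change applicability. The feasibility outcomes, the volume measurement, the daily diary and Q22 are untouched. This should be corrected before analysis, but it does not threaten the study's main conclusions.

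**What to change.** Replace the sentence on not-applicable answers in Section 4 with:

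> Not applicable is recorded with a non-numeric code and is not scored. For the baseline-to-endpoint comparison, each domain score at both visits is the mean of the items answered at both visits, provided at least half of the domain's items qualify; otherwise the domain score is missing and is not imputed.

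Also name the domains or total score to be analysed, state which direction is worse, and report the number of not-applicable answers by visit, so that any net movement is visible. The half-of-items threshold is a judgement and can be changed, provided it is fixed before the data are examined. Leaving such scores unimputed agrees with the missing-data statement in Section 16.

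The cost is a few lines of scoring text and no new data. The downside is that a few subjects may lose a domain score because too few items were answered at both visits.
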